#### **5.10. Dose Delays and Reductions for Lapatinib**

Dose modification guidelines for lapatinib have been developed for the management of selected AEs (Table 10). The investigator must consult the Medical Monitor prior to continuing therapy for any subject requiring a delay of treatment of more than two weeks for any reason, but in general in these circumstances subjects should be withdrawn from treatment permanently.

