**Table 10 Dose modification rules for lapatinib**

Toxicity NCI-CTCAE Grade	During Course of Therapy	Lapatinib Dose Change
Grade 1	Maintain dose	No change
Specific Events of Grade 2/3 Haematology Absolute Neutrophil Count (ANC) <1.5 × 10  /L Platelet count is <100.0 × 10  /L Haemoglobin is <9.0 g/dL (after transfusion if needed) Chemistry For liver AE refer to Section 5.13 Serum Creatinine ≥1.5 mg/dL Calculated Creatinine Clearance <40mL/mins (Appendix 6)	Interrupt treatment until resolved to Grade 0-1, up to 14 days.  If toxicity does not resolve, consult GSK Medical Monitor to determine if it is in the best interest of the subject to continue in the study	1 st appearance Resume 100%  2 nd appearance Resume 100% or dose reduce to 1000mg/day.  3 rd appearance-Resume 100% or dose reduce to 1000mg/day.
Grade 2-Any other event For Cardiac Ejection Fraction and interstitial pneumonitis AEs, refer to Section 5.12.3. For liver AE refer to Section 5.13. For rash refer to Section 5.12.1. For diarrhoea refer to Section 5.12.2 and to Appendix 1	Maintain dose for 1 st and 2 nd appearance  Interrupt treatment until resolves to Grade 0-1, up to 14 days for 3 rd and 4 th appearance	1 st appearance-Maintain dose- No change 2 nd appearance- Maintain dose No change 3 rd appearance – Resume 100% or dose reduce to 1000mg/day 4 th appearance – Resume with a dose reduction to 1000mg/day.
Grade 3 – Any other event For Cardiac Ejection Fraction and interstitial pneumonitis AEs, refer to Section 5.12.3. For liver AE refer to Section 5.13. For rash refer to Section 5.12.1. For diarrhoea refer to Section 5.12.2 and to Appendix 1	Interrupt treatment until resolves to Grade 0-1, up to 14 days.	Any appearance-Resume 100% or Reduce dose to 1000mg permitted in consultation with GSK Medical Monitor.
Grade 4 For Cardiac Ejection Fraction and interstitial pneumonitis AEs, refer to Section 5.12.3 For liver AE refer to Section 5.13. For rash refer to Section 5.12.1. For diarrhoea refer to Section 5.12.2 and to Appendix 1	Interrupt treatment until resolves to Grade 0-1, up to 14 days.	Consult with GSK Medical Monitor to determine if in the best interest of the subject to continue at a dose reduction.

Toxicity grading system according to NCI-CTCAE V4.03

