Continue with supportive care until diarrhoea has resolved (diarrhoea free for 12 hours/bowel pattern return to baseline). Once diarrhoea has resolved, the subject can begin to gradually re-introduce foods from their normal diet.

If diarrhoea recurs following stopping of loperamide treatment, resume loperamide treatment at the dose and schedule recommended above and re-introduce diet modifications. Continue with study treatment.

If Grade 1 diarrhoea persists for  $\geq 2$  weeks, refer to the management guidelines for Persistent Grade 2 Diarrhoea.

## II. CTCAE Grade 2

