**III. Persistent ( $\geq 3$  days/72 hours) Grade 2 Diarrhoea:** hold lapatinib and chemotherapy (if applicable) until diarrhoea resolves ( $<$ Grade 1/return to baseline bowel pattern). If supportive care measures and the interruption of study treatment (i.e., lapatinib and if applicable chemotherapy) are ineffective in treating persistent Grade 1 or Grade 2 diarrhoea, perform stool work-up, CBC, electrolytes and other tests as appropriate, consider consulting with a gastrointestinal specialist.

After diarrhoea resolves ( $\leq$ Grade 1), resume treatment with lapatinib and chemotherapy (if applicable).

**IV. Recurrent Diarrhoea (more than 1 occurrence of Grade 2 diarrhoea):** once the 2nd occurrence of Grade 2 diarrhoea resolves to  $\leq$ Grade 1, consider reducing the dose of lapatinib by 250mg or 1 tablet, unless the lapatinib dose already had been reduced to 750mg. No further dose reduction is recommended for subjects taking lapatinib at 750mg.

3. Consider a dose reduction for chemotherapy (if applicable)

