**Appendix 1 Figure 1 Algorithm for the management of diarrhoea in subjects treated with lapatinib-based therapy**

1. For Grade 1 diarrhoea that persists for 2 weeks or longer, refer to Section III
2. For Grade 2 diarrhoea that persists longer than 3 days/72 hours, refer to Section III
3. For recurrent diarrhoea, refer to Section IV for further management guidelines

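### Appendix 1 holds study drugs until diarrhoea is below Grade 1 but resumes them at Grade 1 or less, and Tables 10 and 11 do not settle which applies to persistent Grade 1

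*Protocol*

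**What the plan says.** Protocol Appendix 1, section III, covers Grade 2 diarrhoea lasting 72 hours or more. Its first sentence tells the site to "hold lapatinib and chemotherapy (if applicable) until diarrhoea resolves ( $<$ Grade 1/return to baseline bowel pattern". The closing paragraph sets the restart at or below Grade 1: "Grade 1), resume treatment with lapatinib and chemotherapy (if applicable".

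Persistent Grade 1 diarrhoea reaches the same rule. For Grade 1 lasting two weeks or more, part A) I of Appendix 1 says to "refer to the management guidelines for Persistent Grade 2 Diarrhoea". The footnotes to Appendix 1 Figure 1 repeat this: "For Grade 1 diarrhoea that persists for 2 weeks or longer, refer to Section III".

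Tables 10 (lapatinib) and 11 (capecitabine) answer differently. Their Grade 1 rows read "Maintain dose", with no time limit and no pointer to Appendix 1. Where treatment is interrupted, Table 10 says "Interrupt treatment until resolves to Grade 0-1, up to 14 days", and Table 11 uses the same restart level. Section 5.12.2.2 asks sites to apply Appendix 1 and these tables together, without an order of precedence.

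Section 5.10 requires a Medical Monitor consultation for a delay of more than two weeks and adds that "in general in these circumstances subjects should be withdrawn from treatment permanently".

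**The concern.** One decision, when to end a hold, has two thresholds within the same section, and a subject at Grade 1 meets one and fails the other. A second conflict is whether a subject with persistent Grade 1 should be held at all. Sites following the same protocol could therefore leave one patient on treatment, restart another and keep a third off treatment.

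The direct consequence is uneven exposure. Compliance with lapatinib and capecitabine is still a secondary endpoint in the SAP (Section 2.6.1.4), and interruptions are summarised in Section 2.7.1.2. Diarrhoea-related dose delays are a secondary endpoint in protocol Table 7, although the SAP's reduced list omits them. Time off both drugs in the first nine weeks may also change the risk of diarrhoea.

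There is also a narrow route to the primary endpoint. Withdrawal before Week 9, or in the SAP on or before the Cycle 4 visit, is imputed as Grade 2 or higher diarrhoea. A long hold for Grade 1 that ends in withdrawal would therefore be scored as a Grade 2 event that never occurred.

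**Working it through.** **1. Thresholds side by side for a subject currently at Grade 1**

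| Source | Rule | Result at Grade 1 |
|---|---|---|
| Appendix 1 III, first sentence | hold until below Grade 1 | stay off |
| Appendix 1 III, closing paragraph | resume at Grade 1 or less | may restart |
| Appendix 1 B) 1, item g (complicated diarrhoea) | hold until Grade 1 or less | may restart |
| Tables 10 and 11, Grade 1 row | no change | never stopped |
| Tables 10 and 11, interruption rows | restart at Grade 0-1, up to 14 days | may restart |

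Read literally, the first line holds uncomplicated diarrhoea to a stricter end point than complicated diarrhoea. That suggests text that was never reconciled, not a deliberate two-step rule.

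**2. Who can be rescored**

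- A subject who enters section III with Grade 2 diarrhoea in the first nine weeks is already a primary event. Neither threshold changes her score.
- A subject with Grade 1 only can be rescored if she is held for more than two weeks (Section 5.9 allows a delay of up to two), withdrawn from treatment after the consultation in Section 5.10, and so withdrawn from the study under Section 4.3.2. She is then imputed as an event under protocol Section 9.3.5 and SAP Sections 2.5.2.1 and 2.5.3, in the ITT and m-ITT analyses.

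**3. Timing**

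Nine weeks are 9 × 7 = 63 days. The route needs at least 14 days of Grade 1 and then more than 14 days of hold, so more than 28 days. 63 − 28 = 35 days, so onset must be by about Week 5. This uses the nominal calendar. The SAP closes the window at the actual Cycle 4 visit.

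**4. Size per subject**

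- Planned design, 70 per arm: 1/70 = 1.4 percentage points.
- Stopped trial: the SAP gives 62 enrolled but no split by arm. Assuming an even split, 62/2 = 31 and 1/31 = 3.2 points.

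**5. Scale against the planned power (illustration only)**

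Table 21 is reproduced by the pooled-variance normal approximation without continuity correction, at one-sided 0.025:

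power = Φ{[d − 1.96·√(2p̄(1−p̄)/70)] / √([p₁(1−p₁) + p₂(1−p₂)]/70)}

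For 20% v 6% this gives 69.6% (stated 69%), and for 20% v 7% it gives 61.6% (stated 61%). One added point in the octreotide arm alone therefore costs about 8 points of planned power. One added point in both arms (21% v 7%) gives 66.9%, a loss of about 3. The documents give no rate of such withdrawals, so these figures show sensitivity and do not predict a loss.

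**The case against.** The case against a serious finding is substantial, and most of it stands.

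- **The primary endpoint is rarely touched.** Section III mainly serves subjects with Grade 2 diarrhoea, who are already events. A reader might infer that the conflicting thresholds affect the primary result generally. They do not.
- **Withdrawal is not automatic.** Section 5.10 qualifies it as the general course after a consultation. A site that uses the tables' restart level would already have restarted a Grade 1 subject.
- **The rule does not simply cancel itself.** Because a Grade 1 subject already meets the resume condition, a reader might infer that she would be restarted at once. Section III itself refers to treatment interruption that has failed to control persistent Grade 1 or Grade 2 diarrhoea, so an interruption for persistent Grade 1 is expected.
- **Part of the conflict is general against specific.** The tables cover all toxicities, while Appendix 1 continues treatment for Grade 1 and adds an exception at two weeks. Appendix 1 also calls itself recommended guidance. But the Grade 2 to 4 rows refer to Appendix 1 and the Grade 1 row does not, so sites are not told that the exception exists.
- **There is some protection in the analysis.** The per-protocol analysis uses no imputation, although the SAP makes it descriptive only. The same rules apply to both arms and the documents show no differential effect, although treatment is open-label.

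The Appendix 1 Figure 1 algorithm is not visible in the text reviewed, so whether it settles the threshold could not be checked. None of these points removes the two thresholds inside section III.

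**Conclusion.** The inconsistency is real, stands in current protocol text and should be resolved. Its main effect is uneven holding and restarting of study drugs, and so of exposure, dose delays and compliance. Its effect on the primary endpoint is confined to an uncommon case: Grade 1 only, onset by about Week 5, a hold of more than 14 days, then withdrawal before Cycle 4. Each such subject counts for 1.4 points at 70 per arm, or about 3.2 points if the 62 enrolled split evenly.

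The number affected cannot be derived from the documents. A reader might multiply the share with maximum Grade 1 diarrhoea in EGF111438 (67/269) by the share of durations over 10 days (44/113) and call the result an upper bound. It is not one. It assumes that grade and duration are independent; without that, the overlap could reach 44/269 = 16.4% on the known durations. Those durations cover all grades and are counted from 10 days rather than 28, and the product says nothing about withdrawal. Nor do the documents show whether any subject took this route.

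**What to change.** Reconcile Appendix 1 section III, the persistent Grade 1 referral in Appendix 1 A) I and the Figure 1 footnote with the Grade 1 and restart entries of Tables 10 and 11. State one hold threshold and one restart threshold, and say which source governs when they differ. The sponsor's clinical team should choose the thresholds. The cost is protocol wording and a site letter, a route that Sections 3.1 and 5.12 already provide.

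Enrolment has stopped, so wording cannot change past conduct and the analysis needs its own step. Identify withdrawals on or before the Cycle 4 visit that followed a delay for Grade 1 diarrhoea only, and report their number by arm. Add a sensitivity analysis of the primary endpoint in which they are not imputed as Grade 2 or higher events. The eCRF already records diarrhoea grade, dose-delay dates and withdrawal (Sections 5.8 and 7.1.6), so the cost is one derived flag and one table. Specify it before database lock, or label it as a deviation from the SAP in the study report.

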## **B) Complicated Diarrhoea**

**1. CTCAE Grade 3 or Grade 1 or 2 with complicating features (severe cramping, severe nausea/vomiting, decreased performance status, fever, sepsis, Grade 3 or 4 neutropenia, frank bleeding, dehydration)**

- a. Subject **must** call physician immediately for any complicated severe diarrhoea event
- b. If loperamide has not been initiated, initiate loperamide immediately: Initial dose 4mg followed by 2mg every 2 hours or after every unformed stool
- c. Refer to the dietary modification recommendations for Grade 1 and Grade 2 uncomplicated diarrhoea
- d. For dehydration use intravenous fluids as appropriate, if subject presents with severe dehydration administer octreotide
- e. Perform stool work-up, CBC, electrolytes and other tests as appropriate
- f. Administer antibiotics as needed (example fluoroquinolones), especially if diarrhoea is persistent beyond 24 hours or there is fever or Grade 3-4 neutropenia
- g. Hold lapatinib and chemotherapy (if applicable) until symptoms resolve to  $\leq$ Grade 1 and reintroduce lapatinib at a reduced dose (unless dose had been reduced to 750mg, contact medical monitor for further guidance)

- i. Consider a dose reduction for chemotherapy (if applicable)
4. Supportive care and other interventions should be continued until diarrhoea free (i.e., <Grade 1/bowel patterns returned to baseline) for 24 hours
5. Intervention may require hospitalisation for subjects most at risk for life threatening complications

[figure not shown]
## **II CTCAE Grade 4**

Subject must call physician immediately for any Grade 4 diarrhoea event

1. Discontinue treatment with lapatinib, hold chemotherapy (if applicable)
2. If loperamide has not been initiated, initiate loperamide immediately: Initial dose 4mg followed by 2mg every 2 hours or after every unformed stool
3. For dehydration use intravenous fluids as appropriate, if subject presents with severe dehydration administer octreotide
4. Perform stool work-up, CBC, electrolyte and other tests as appropriate
5. Recommend consulting with gastrointestinal specialist
6. Administer antibiotics as needed (example fluoroquinolones), especially if diarrhoea is persistent beyond 24 hours or there is fever or Grade 3/4 neutropenia
7. Supportive care and other intervention should be continued until diarrhoea free (i.e., <Grade 1/bowel patterns returned to baseline) for 24 hours
8. Intervention may require hospitalisation for subjects most at risk for life threatening complications

Refer to and follow the recommended supportive care guidelines in the previous sections and as depicted in [Appendix 1 Figure 1](#).

**Appendix 1 Figure 1 Algorithm for the management of diarrhoea in subjects treated with lapatinib-based therapy**

1. For Grade 1 diarrhoea that persists for 2 weeks or longer, refer to Section III
2. For Grade 2 diarrhoea that persists longer than 3 days/72 hours, refer to Section III
3. For recurrent diarrhoea, refer to Section IV for further management guidelines

## 12.2. Appendix 2 FACIT-D Questionnaire

[figure not shown]
The FACIT-D questionnaire (version 4, English original) is available in two forms with different dates: '16 Nov 2007' and '09 June 2013'. These two forms have minor differences in question phrasing and format. Both forms are fully validated and the minor differences between two forms do not affect the quality of data collection and analysis. In this study, the languages translated based on 'English FACIT-D version 4 (dated 16 Nov 2007)' are Arabic, French, Hebrew, Italian and Polish. The languages translated based on 'English FACIT-D version 4 (dated 09 June 2013)' are Czech, Greek, Russian and Traditional Chinese.

[figure not shown]
This appendix provides an example of the questionnaire 'English FACIT-D version 4 (dated 09 June 2013)'.

[figure not shown]
Below is a list of statements that other people with your illness have said are important. **Please circle or mark one number per line to indicate your response as it applies to the past 7 days.**

[figure not shown]

[figure not shown]

[figure not shown]

[figure not shown]

S  
S

r

## 12.4. Appendix 4 Eastern Cooperative Oncology Group Performance Status

The scale and criteria summarised [Appendix 4 Table 1](#) are designed to assess how a subject's disease is progressing and to assess how the disease affects activities of daily living of the subject.

## **12.5. Appendix 5 Country Specific Requirements**

No country-specific requirements exist.

## 12.6. Appendix 6 Cockcroft-Gault Equation for Calculating Creatinine Clearance

Creatinine clearance can be calculated from serum creatinine values by two formulas.

To calculate as mg/dL:

$$\begin{aligned} \text{Calculated creatinine} \\ \text{clearance (mL/min)} = & \frac{(140 - \text{age [years]}) \times \text{weight (kg)}}{72 \times \text{serum creatinine (mg/dL)}} \\ \text{Female subjects: multiply by 0.85} \end{aligned}$$

To calculate as  $\mu\text{mol/L}$ :

[figure not shown]
$$\begin{aligned} \text{Calculated creatinine} \\ \text{clearance (mL/min)} = & \frac{(140 - \text{age [years]}) \times \text{weight (kg)} \times 88.4}{72 \times 1 \times \text{serum creatinine } (\mu\text{mol/L})} \\ \text{Female subjects: multiply by 0.85} \end{aligned}$$

## 12.7. Appendix 7 Liver Chemistry Monitoring, Interruption Stopping and Follow-up Criteria

Appendix 7 Figure 1 Liver safety algorithm

## 12.8. Appendix 8 Protocol Changes

### Amendment 1

**Protocol Amendment 01 applies to all site(s) participating in the conduct of the study**

#### Summary of changes and rationale:

Change	Rationale
Prior treatment with lapatinib was added as an exclusion criterion.	It is possible that prior treatment with lapatinib might influence the subjects' perception of the tolerability of lapatinib, or the subjects' susceptibility to lapatinib-associated diarrhoea.
Additional detail was provided for dermatological monitoring.	The protocol was updated to include the GSK lapatinib dermatological assessment guidelines (version 4.0, 10 March 2014). The frequency of skin examination was modified to be consistent with recommendations in the lapatinib SPC.
Secondary endpoints related to patient reported outcomes were updated.	The Diarrhoea Management Diary was revised after the LAP117314 protocol was finalised (17 February 2014). The patient-reported endpoints and objectives were amended to be consistent with the revised Diarrhoea Management Diary.
The schedule for completion of the Diarrhoea Management Diary and FACIT-D was clarified.	Information has been provided to describe and clarify the schedule for completion of the Diarrhoea Management Diary and FACIT-D at the baseline visits and during treatment with lapatinib and capecitabine.
The schedule of study visits relative to the week numbers and cycles of treatment with lapatinib and capecitabine was clarified	The Diarrhoea Management Diary and FACIT-D refer to 'Week' of treatment and the protocol Time and Events table refers to 'Cycle' of treatment. Information has been provided to describe and clarify the relationship between 'Week' and 'Cycle' of treatment.
The use of octreotide s.c. within the diarrhoea management guidelines was clarified	The protocol includes the GSK diarrhoea management guidelines, which recommend the use of octreotide as a second line treatment option for diarrhoea refractory to treatment with loperamide. Additional guidance has been provided concerning the use of octreotide s.c. in subjects randomised to receive treatment with octreotide LAR.

Change	Rationale
Typographical errors have been corrected; Time and Events table content has been update; format changes have been made.	These changes have been made to improve the quality of the protocol, and are listed in detail in this appendix.

### Detail of changes

- The detail of changes is presented in the order in which the change appears in the protocol.
- ‘Original’ refers to content of the protocol dated 17 February 2014.
- ‘Amended’ refers to the content of the protocol as updated in Amendment 01.
- Text deleted from the original protocol is presented as a ~~strikethrough~~ font.
- The location of the changes in the text of the protocol is identified by section number and title, followed by paragraph number and sentence number if required.
- Minor changes to table content are identified by table number, followed by row number and column number.
- More extensive changes to tables are presented as ‘Original’ table content, followed by ‘Amended’ table content.
- Changes to section numbers and table numbers subsequent to amendment changes are not recorded in the appendix, unless this clarifies the location of the change.

### Table of contents

The Table of Contents was updated.

### List of abbreviations

Added:

DMD	Diarrhoea Management Diary
DSS	Diarrhoea symptom subscale

Deleted:

<del>IWR</del>	<del>Interactive web response</del>
<del>NG</del>	<del>Next generation</del>

### Minor Typographical changes

These changes may also occur in sections of text which have been more extensively modified, summarised in other sections of this appendix.

‘Diarrhoea diary’ has been changed to ‘Diarrhoea Management Diary’ or ‘DMD’ in the following locations:

Location	Paragraph	Line
Protocol Summary: Rationale	7	15/16

Location	Paragraph	Line
Protocol Summary: Objectives	3	2, 4
Section 1.2 Study rationale	6	1
Section 1.2 Study rationale	7	1, 2
Section 2 Objectives and Endpoints	3	2, 4, 5
Section 3.1 Study design	14	1
Section 3.2 Discussion of design	12	2, 4, 6, 7
Section 5.8 Treatment compliance	3	2, 3
Time and Events Table 16	Footnote	6
Time and Events Table 17	Footnote	6
Section 7.1.6 Assessments every 3 weeks	Bullet list	Bullet point 9
Section 7.1.8 Study completion or early withdrawal	Bullet list	Bullet point 7
Section 8 Data Management	3	1
Section 9.3.5.1 Efficacy analyses	1	6

The term ‘every week’ was added to clarify the frequency for completing the DMD in the following locations:

Location	Paragraph	Line
Protocol Summary: Objectives	3	2
Section 2 Objectives and Endpoints	3	2
Section 3.1 Study design	14	1

The term ‘every 3 weeks’ was added to clarify the frequency for completing the FACIT-D in the following locations:

Location	Paragraph	Line
Protocol Summary: Objectives	3	2
Section 2 Objectives and Endpoints	3	2
Section 3.1 Study design	14	1

